7.9.1.4 Determination of Patients/Data for Analysis

The Enrolled Population will be included in the descriptive statistics shown in Table 1.

At each FU visit, the subset of subjects of the Enrolled Population that at that visit will have a reason for referral will be used to compute the descriptive statistics shown in Table 2 and the odds ratios of referral.

7.9.2 Secondary objective 1: Proportion of post-acute MI patients who are indicated for an ICD/CRT-D

Characterize the proportion of post-acute MI patients who are known to be indicated for an ICD/CRT-D within 12 months post-MI

7.9.2.1 Hypothesis

There are no hypotheses for this objective, as this is a characterization objective.

7.9.2.2 Endpoint definitions

The endpoint will be defined as whether a subject was indicated for an ICD/CRT-D device during follow-up.

7.9.2.3 Analysis methods

Among all subjects referred, the proportion of subjects that had an SCD risk stratification visit will firstly be computed, followed by the proportion of subjects that were indicated for ICD/CRT-D implant. Details of the computations are described below.

First, at each follow-up visit, among all patients who were referred for SCD risk stratification, the proportion of those who had an SCD risk stratification visit will be computed.

For any given follow-up visit (3 months, 6 months, 12 months), the denominator will be patients referred for SCD risk stratification up to the given visit and the numerator will be all patients that, among the patients included in the denominator, will have an SCD risk stratification visit

In the referral CRF, the patients included in the denominator will be a composite of the below:

- (a) ***all patients that were referred but did not have any ICD risk stratification visit at any previous follow-up visit.*** That is, within the referral CRF form, all subject that at any of the previous visits will have answer “yes” to the question “has the subject been referred or invited for SCD risk stratification?” and answer “no” to the question “was the SCD visit performed?”.
- (b) ***all patients being referred at the given visit.*** That is, within the referral CRF form, all subject that at a given visits will have answer “yes” to the question “has the subject been referred or invited for SCD risk stratification?”.

The subjects included in the numerator will be all subjects part of the denominator that will have answer “yes” to the question “was the SCD visit performed?”.

For example, at the 6 months visit, the numerator will be all patients that had their SCD risk stratification visit at the 6 months visit and the denominator will be all patients who were referred but did not have their SCD risk stratification visit within the 3 months visit window and of all patients that were referred at the 6 months visit.

The results will be shown in a table similar to table 4 below:

Table 4: Number (%) of subject that had their SCD risk stratification visit

	3 months visit	6 months visit	12 months visit
Region 1	XX/XX (XX.XX%)	XX/XX (XX.XX%)	XX/XX (XX.XX%)
Region 2	XX/XX (XX.XX%)	XX/XX (XX.XX%)	XX/XX (XX.XX%)
...
Overall	XX/XX (XX.XX%)	XX/XX (XX.XX%)	XX/XX (XX.XX%)

It may also happen that a patient might have an SCD risk stratification visit without having been referred, for example, patients who had an SCD risk stratification visit for secondary prevention. An additional table will then be created to show, for each visit, the number of subjects that were not referred but had an SCD risk stratification visit and among those, the proportion of subjects that had a reason for referral.

Second, the proportion and Wilson score 95% CI of subjects recommended for ICD/CRT-D at the three months visit, at the 6 months and at the 12 months visits will be computed overall and by region, for the Enrolled Population and for the subjects in the numerator in table 3 above, that is, all subjects that have had an SCD risk stratification visit (called in table 4 below “SCD risk stratification Population””).

A SAS code similar to the example SAS code shown in Section 7.9.1.3 will be used. For each follow up visit, the results will be shown in a table similar to Table 5 below.

Table 5: Proportion (95% CI) of subjects indicated to receive ICD/CRT-D, at visit X

Region	Enrolled Population		SCD risk stratification population	
	n/N (%)	95% CI	n/N (%)	95% CI
Region 1	XX/XX (XX.XX%)	(XX.XX% - XX.XX%)	XX/XX (XX.XX%)	(XX.XX% - XX.XX%)
...
Overall	XX/XX (XX.XX%)	(XX.XX% - XX.XX%)	XX/XX (XX.XX%)	(XX.XX% - XX.XX%)

Where n is number of the subjects “recommended for ICD/CRT-D” and N is either the Enrolled Population or the SCD risk stratification population.

In addition to the above analyses, logistic regression models similar to the example model in Section 7.9.1.3 might be fitted overall and by region, to estimate the odds ratios of being indicated for an ICD/CRT-D, depending on different factors, such as sex, age, specialty of physician who performed the ICD/CRT-D risk stratification, type of device received – ICD or CRT-D, PCI versus non-PCI patients, STEMI versus non-STEMI patients . Results will be displayed either by means of either tables or of plots.

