9.3. Schedule of Events

Clinical data will be collected at the Baseline 3 month, 6 month, 12 month, and exit visits. In addition if applicable, clinical data will be collected with an exit or death, as well as unscheduled visits. Device data will be collected from device interrogations on Medtronic devices received during the period between the enrollment and exit until study closure; for non-Medtronic devices, device data will not be collected. Data will be collected using eCRFs using an electronic data management system for clinical studies. In addition to eCRF data, non-eCRF data will be collected including device interrogation files (for Medtronic implanted devices only). Surveys may also be used throughout the study.

Data will be stored in a secure, password-protected database, which will be backed up nightly. Data will be reviewed using programmed and manual data checks. Data queries will be made available to study sites for resolution. Study management reports will be generated by Medtronic to monitor data quality and study progress. At the end of the study, the data will be frozen and retained indefinitely by Medtronic. Data Collection requirements are summarized in the table 2 below.

Table 2 Data Collection and study procedure requirements at subject visit

Study Procedure	Baseline	3 month visit	6 month visit	12 month visit	Study Exit
Patient informed consent	X				
Eligibility Verification (Inclusion/ exclusion assessment)	X				
Subject Demographics	X				
Acute MI information	X				
Medical History	X				
Cardiovascular Medications	X	X			
LVEF measurement	X	X*	X (collect if performed as per SOC)	X (collect if performed as per SOC)	
ECG	X	X (collect if performed as per SOC)	X (collect if performed as per SOC)	X (collect if performed as per SOC)	
Referral Status		X	X	X	X
Implant Status (if applicable)		X (if subject receives or has received device implant)	X (if subject receives or has received device implant)	X (if subject receives or has received device implant)	X (if subject receives or has received device implant)
Device Interrogation File (pdd) or CareLink Transmission for subjects implanted with Medtronic device only		X	X	X	X
Adverse Event	As they occur				
System Modification					
Study Deviation					
Subject Death					

* The LVEF measurement needs to be performed ≥ 40 days post-acute MI for MI subjects without revascularization, or ≥ 90 days post-revascularization for post-MI subjects with revascularization done.

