9.7. Study Exit

At 3-month follow-up, if a subject has an LVEF $\geq 50\%$, the subject will be exited from the study. Subject who remain in the study after 3-month follow-up should remain in the study until the 12-month follow-up is completed or until all data required to meet study objectives have been collected (whichever comes first). Either an in-office visit or phone call is required for study exit.

A study exit eCRF is required for all subjects. Prior to exiting a subject from the study, it is recommended to follow the subject until all AEs are resolved. Following exit, subjects will continue to receive standard medical care. Upon exiting from the study, no further study data will be collected or study visits will occur for the subject. Exited subjects will not be replaced with newly enrolled subjects.

Subjects are urged to remain in the study as long as possible, but may be exited from the study for any of the following situations:

- Study closure
- Subject lost to follow-up (refer to Section 9.11.1)
- Subject did not meet inclusion/exclusion criteria
- Subject did not provide consent or data use protection authorization
- Subject chooses to withdraw (refer to section 9.11.2 for more information)
- Investigator deems withdrawal necessary (e.g. medically justified, inclusion/exclusion criteria not met)
- Subject exited study at the 3 months visit if the 3-month LVEF is $\geq 50\%$
- Subject completed study after 12 months visit
- Subject Death

For study exit visits the following information is required:

- Reason for exit
- Final interrogation file (or CareLink transmission) for subjects implanted with Medtronic device
- Cardiovascular Adverse events, Study Deviations and System Modification

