11.3. Subject Death

11.3.1. Death Data Collection

All subject deaths must be reported by the investigator to Medtronic on an AE (AE with the outcome of fatal) and Death CRFs as soon as possible after the investigator first learns of the death. Exit CRF also needs to be completed.

If any Medtronic system component is returned to Medtronic, internal return product reporting systems may be used to gather additional information about the returned device/component.

A copy of the death certificate, if available and allowed by state/local law, should be sent to the Medtronic study team. When a death occurs in a hospital, a copy of the death summary report and all relevant hospital records should be sent to the Medtronic study team, if available. If an autopsy is conducted, the autopsy report should also be sent to the Medtronic study team if available and allowed by state/local law. When the death occurs at a remote site, it is the investigative site's responsibility to attempt retrieval of information about the death. Additionally, device disposition information should be updated. In summary, the following data will be collected:

- Date of death
- Detailed description of death
- Cause of death
- Device interrogation (or CareLink transmission) for subjects implanted with Medtronic device
- Death summary/hospital records (if available and allowed by state/local law)
- Autopsy report (if available and allowed by state/local law)
- Death certificate (if available and allowed by state/local law)

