12.5. Missing data

Missing data will not be imputed. For survival endpoints, subjects who do not meet the endpoint and exit or die prior to completing follow-up will be censored at the date of death or exit for endpoints that do not include the type of death the subject experienced (e.g. cardiovascular death).

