7.9.3.3 Analysis methods

At each follow-up visit (3 months, 6 months, 12 months), the proportion of subjects who received an ICD/CRT-D will be computed.

The numerator will be the number of subjects who were implanted at a given follow up visit. In the Implant CRF, these subjects will have answer “yes” to the question “Has the subject received an ICD or CRT-D?”.

The denominator will be either the Enrolled Population or a composite of the below:

- (a) ***all patients meeting an indication for implant and not having been implanted at the previous visits.*** That is, within the Implant CRF form, all subject that at any previous visits will have answer “yes” to the question “did the subject meet an indication for an ICD or CRT-D?”, and at all previous visits will have answer “no” to the question “has the subject received an ICD or CRT-D?”
- (b) ***all patients meeting an indication for implant at the given visit.*** That is, within the referral CRF form, all subject that at a given visit will have answer “yes” to the question “did the subject meet an indication for an ICD or CRT-D?”

A SAS code similar to the example SAS code shown in Section 7.9.1.3 will be used. Separately for each follow up visit, the results will be shown in a table similar to Table 6 below, where “Indicated for an ICD/CRT-D” is the denominator above.

Table 6: Proportion (95% CI) of subjects who receive ICD/CRT-D at visit X

	Enrolled Population		Indicated for an ICD/CRT-D Population	
Region	n/N (%)	95% CI	n/N (%)	95% CI
Region 1	XX/XX (XX.XX%)	(XX.XX% - XX.XX%)	XX/XX (XX.XX%)	(XX.XX% - XX.XX%)
Region 2	XX/XX (XX.XX%)	(XX.XX% - XX.XX%)	XX/XX (XX.XX%)	(XX.XX% - XX.XX%)
...
Overall	XX/XX (XX.XX%)	(XX.XX% - XX.XX%)	XX/XX (XX.XX%)	(XX.XX% - XX.XX%)

In addition to the above analyses, logistic regression models similar to the example model in Section 7.9.1.3 might be fitted overall and by region, to estimate the odds ratios of being implanted, depending on different factors, such as age, gender, specialty of physician who implanted, type of device received – ICD or CRT-D, PCI versus non-PCI, STEMI versus non-STEMI. Results will be displayed either by means of either tables or of plots.

Additional analysis:

A competing risk event curve with accompanying 95% confidence bounds and mortality accounted for, will be produced for each region, to assess a subject's time from enrollment to:

- (a) Having met the referral criteria;
- (b) Having been referred;

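### SAP Tables 4 to 6 take no events from the exit or death record, and Protocol 9.7 does not ask for them, so the indication and implant proportions are understated

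*SAP*

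**What the plan says.** SAP table numbers below are those of the captions.

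**Collection.** Protocol 9.3 makes exit a data-collection point: "Clinical data will be collected at the Baseline 3 month, 6 month, 12 month, and exit visits". In Protocol Table 2 the row "Referral Status" is marked at 3, 6 and 12 months and at Study Exit. The implant-status row is marked at the same four points, at exit with "X (if subject receives or has received device implant"). Protocol 9.7 then gives its own list, introduced by "For study exit visits the following information is required". It contains the reason for exit, the final interrogation or transmission for Medtronic devices, and cardiovascular adverse events, deviations and system modifications. Referral and implant status are absent, although both head the follow-up list in Protocol 9.6.1. For deaths, Protocol 11.3.1 adds that "Exit CRF also needs to be completed"; its own list of death data names neither item.

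**Analysis.** SAP 7.9.2.3 defines the stratification proportion with "For any given follow-up visit (3 months, 6 months, 12 months") and reports indication at those visits. SAP 7.9.3.3 says of implants: "The numerator will be the number of subjects who were implanted at a given follow up visit". In both sections, part (a) of the denominator carries forward subjects referred or indicated earlier who were still awaiting the next step. The endpoints in SAP 7.9.2.2 and 7.9.3.2 are worded as an indication or implant at any time in follow-up. SAP 7.9.3.3 also plans competing-risk curves (a) to (e), timed from enrollment to the date of each event.

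**The concern.** A site that works from Protocol 9.7 can leave out what Protocol Table 2 requires, and the same section ends data collection at exit. A site that works from Protocol Table 2 records the status, but no SAP visit table reads it. The SAP uses the exit form only to classify deaths and exits (7.9.1.3).

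The study exists to describe where patients drop out of the care pathway. A subject who was implanted and then died before the next visit would be reported as untreated, or as indicated and untreated. The loss falls on subjects who die or withdraw, so it cannot be assumed unrelated to outcome. It always pushes the proportion down, so pooling regions does not average it out.

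**Working it through.** **1. Which intervals are exposed.** By the visit windows (Protocol Table 3, SAP Table 1), the 3-month window closes at day 120 and the 6-month window opens at day 150. The 6-month window closes at day 210 and the 12-month window opens at day 335, a gap of 335 - 210 = 125 days. Exits for LVEF of 50% or more at 3 months, and completion at 12 months, coincide with a visit and are not exposed. Deaths, withdrawals and other early exits are.

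**2. How the stated rules treat three subjects.**
- *Not indicated at 6 months, then indicated and implanted, then withdraws before month 12.* In the 12-month Enrolled Population columns of Tables 5 and 6 this subject is in N and not in n.
- *Indicated but not implanted at 6 months, implanted at month 8, dies at month 10.* Part (a) of the Table 6 indicated denominator carries the subject into month 12, with no rule removing those who have left. The implant never reaches the numerator.
- *Referred at 3 months, stratified later, leaves before the 6-month visit.* Part (a) of Table 4 keeps the subject in the 6-month denominator, and the numerator misses the stratification visit.

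**3. Where the rules do no such harm.** Table 3 counts only subjects with a referral criterion met at the visit, so someone who has left is in neither part of the fraction. A subject first referred after the last visit is likewise in neither part of Table 4.

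**4. The plan's own figures.** The exact binomial probability that the 95% Wilson half-width is at most 0.125 at a proportion of 0.70 is 0.784 for n = 53 and 0.897 for n = 54. So 54 is the first n to reach 0.80. Then 54 / 0.30 = 180 and 180 / 0.90 = 200 per region. The plan's figures reproduce. The 10% loss used there covers only enrollment to 3 months; no later rate is given.

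**5. Size on the Enrolled Population.** Let e be the share of enrolled subjects leaving between visits, and s the share of those who had the event in question since their last visit. Both are assumptions, applied to one endpoint at a time. The shortfall is e × s:
- 0.05 × 0.05 = 0.0025: 0.25 points, 0.5 subjects in 200
- 0.10 × 0.10 = 0.010: 1.0 point, 2 subjects in 200
- 0.10 × 0.20 = 0.020: 2.0 points, 4 subjects in 200
- a wider extreme, 0.20 × 0.30 = 0.060: 6.0 points, 12 subjects in 200

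**6. Against sampling error.** Take the middle case, 2 missed implants in a region of 200.
- Assumed 20 recorded: 10.0% (Wilson 95% CI 6.6 to 14.9) should be 22/200 = 11.0% (7.4 to 16.1). The share missed is 2/22 = 9%.
- Assumed 10 recorded: 5.0% (2.7 to 9.0) should be 6.0% (3.5 to 10.2). The share missed is 2/12 = 17%.

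Within one region this is well inside the interval. In the Overall row with 1,200 subjects, the half-width at 10% is about 1.96 × √(0.10 × 0.90 / 1,200) = 1.7 points, so a 1-point shortfall is more than half of it.

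**7. The carried-forward denominators** are smaller, so each missed event weighs more. The plan's assumptions imply 54 × 0.70 = 37.8 referred subjects per region at 3 months. If the Table 4 denominator were about 38, one missed stratification visit would cost 1/38 = 2.6 points.

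**The case against.** The best defence is that nothing is shown to go uncollected. Protocol 9.3 presents Protocol Table 2 as the summary of data requirements, also provides for data at exit, death and unscheduled visits, and is not cancelled by 9.7. The case report forms are under separate cover, so what the exit form asks cannot be seen. The curves use event dates and would count a recorded event. SAP 5.1 already moves a referral found at a late visit to the next visit, which resembles the rule proposed here. The affected group is narrow, and subjects lost to follow-up may yield nothing under any list.

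Most of this stands, and it limits the point. It does not rescue Tables 4 to 6: even if every site records status at exit, those tables count only what is found at the three visits. The late-visit rule in SAP 5.1 concerns out-of-window visits and does not mention exits.

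Three stronger readings are tempting and not supported:
- **That these events vanish from the whole analysis.** The curves lose them only if the dates are not collected at exit or if the curves are built from visit forms alone; the SAP names no source form. If status is recorded, the tables miss the event and the curves can catch it. If it is not, both miss it. The two harms do not apply to the same event.
- **That the primary result is biased in the same way.** Step 3 shows it is not, and SAP Table 2 lists deaths and exits as separate groups.
- **That everyone who leaves is censored as event-free.** Protocol 12.5 says "subjects who do not meet the endpoint and exit or die prior to completing follow-up will be censored at the date of death or exit", which applies only to those without the endpoint. For the curves in SAP 7.9.3.3, death is coded as a competing event.

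**Conclusion.** The point holds for Tables 4 to 6. Followed as written, the rules understate the indication and implant proportions on the Enrolled Population, and the stratification and implant proportions on the carried-forward denominators, relative to endpoints defined over the whole of follow-up. The conflict between Protocol Table 2 and 9.7 puts the curves at risk as well, but only where exit dates go unrecorded.

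The direction follows from the rules; the size does not. Under assumed e = 5-10% and s = 5-20% it is 0.25-2.0 points for each endpoint separately. That is small beside the uncertainty in one region, but not negligible for an infrequent outcome such as implant or in the pooled row. The documents give neither e nor s.

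**What to change.** - **Protocol 9.7:** add referral status and implant status, with event dates, to the exit list so that it matches Protocol Table 2.
- **SAP 7.9.2.3 and 7.9.3.3:** count events recorded on the exit or death record at the next scheduled visit.
- **SAP 7.9.3.3:** state that these records feed curves (b) to (e).
- **Tables 4 and 6:** state how subjects who have died or left are handled in part (a) of each denominator.

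The cost is a little more form completion, for items Protocol Table 2 already requires, and some programming. No visit or procedure is added. For some subjects lost to follow-up nothing will be recoverable, so a smaller shortfall will remain.

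### The form-level rule for denominator group (a) of SAP Table 4 contradicts its own definition and, if programmed as written, gives a wrong 12-month proportion

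*SAP*

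**What the plan says.** SAP 7.9.2.3 describes the Table 4 denominator in four places.

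- **Opening sentence:** "the denominator will be patients referred for SCD risk stratification up to the given visit". This is cumulative.
- **Definition of group (a):** "all patients that were referred but did not have any ICD risk stratification visit at any previous follow-up visit". This is a set of subjects still waiting.
- **Form-level rule for (a),** introduced as a restatement of that definition: "all subject that at any of the previous visits will have answer" yes to having been referred and no to the stratification visit having been performed.
- **6-month worked example:** "the denominator will be all patients who were referred but did not have their SCD risk stratification visit within the 3 months visit window", plus the subjects referred at 6 months.

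Group (b) adds subjects referred at the visit in question.

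The numerator rule reads "The subjects included in the numerator will be all subjects part of the denominator that will have answer" yes to the stratification visit having been performed. It does not say at which visit the yes must be recorded. The 6-month example counts stratification at that visit.

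SAP 7.9.3.3 sets up the implant table (Table 6) in the same way: indicated earlier, not yet implanted. There the rule requires that the subject "at all previous visits will have answer" no to having received a device.

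**The concern.** The definition of (a) excludes anyone who already had a stratification visit at any earlier follow-up. The form-level rule needs only one earlier visit with the pair referred = yes, stratification visit = no. The two agree when there is a single previous visit and can differ when there are two, which happens only in the 12-month column.

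A subject who was referred and pending at month 3 and stratified at month 6 still has the qualifying month-3 record at month 12. That subject is no longer waiting but is kept in the 12-month denominator.

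Table 4 describes whether referred patients go on to be stratified, one step in the care pathway the study sets out to characterise. Its numerator also defines the stratified population used as the second denominator in Table 5, so an unspecified numerator visit can carry over there.

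**Working it through.** The documents give no figure for Table 4 (its cells are placeholders), so there is nothing to reproduce. The check is logical first, then numerical on assumed counts.

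**Step 1. All visit patterns.** Referral can first occur at 3, 6 or 12 months, and stratification at that visit, at a later visit or never. That gives 4 + 3 + 2 = 9 patterns. Membership of the 12-month denominator, groups (a) and (b) together:

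| Referred | Stratified | Definition | Rule as written | No at all previous visits since referral |
|---|---|---|---|---|
| 3 | 3 | out | out | out |
| 3 | 6 | **out** | **in** | **out** |
| 3 | 12 | in | in | in |
| 3 | never | in | in | in |
| 6 | 6 | out | out | out |
| 6 | 12 | in | in | in |
| 6 | never | in | in | in |
| 12 | 12 | in | in | in |
| 12 | never | in | in | in |

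One pattern of nine is misclassified. The 6-month denominator is the same under all three rules, and at 3 months there is no previous visit.

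**Step 2. Small illustration (all counts assumed).** 20 subjects are pending at month 3, 15 are stratified by month 6, 3 of the other 5 by month 12, with no new referrals.

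- Definition: denominator 20 − 15 = 5, numerator 3, so 3/5 = 60%.
- Rule as written, yes counted at the 12-month visit: 3/20 = 15%.
- Rule as written, yes counted at any visit so far: (15 + 3)/20 = 18/20 = 90%.

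**Step 3. Regional scale.** SAP 6.1 plans 54/0.30 = 180 subjects at 3 months and 180/0.90 = 200 enrolled, with 70% of the 54 referred: 54 × 0.70 = 37.8, about 38. Everything else here is assumed:

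- Half of the 38 are stratified at month 3, leaving 19 pending.
- There are 4 new referrals at month 6 and 2 at month 12, half of each stratified at once.
- Half of those still outstanding are stratified at month 12.
- Counts are rounded to whole subjects, halves to the even number.

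| Share of the 19 stratified at month 6 | Definition | As written, yes at month 12 | As written, yes at any visit |
|---|---|---|---|
| 20% (4) | 9/19 = 47.4% | 9/23 = 39.1% | 13/23 = 56.5% |
| 50% (10) | 7/13 = 53.8% | 7/23 = 30.4% | 17/23 = 73.9% |
| 80% (15) | 4/8 = 50.0% | 4/23 = 17.4% | 19/23 = 82.6% |

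With 50% stratified at month 6 and the month-3 share set to 0%, 25% or 75%, the definition gives 47.8%, 50.0% and 55.6%. The literal rule gives 26.2%, 28.1% and 35.7% with the yes at month 12, or 71.4%, 71.9% and 71.4% with the yes at any visit.

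**Step 4. The cumulative sentence.** In the 50% row, everyone referred so far is 38 + 4 + 2 = 44. The literal rule gives 23 = 44 − 19 − 2: it drops the 19 stratified at month 3 and the 2 referred and stratified at month 6, but keeps the 10 referred at month 3 and stratified at month 6. So it yields neither the waiting set (13) nor the cumulative set (44).

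**The case against.** The strongest reply is that the right rule is already in the text. The form-level sentence is offered as an explanation of the definition, and the 6-month example removes subjects already stratified, so a careful programmer would follow the definition. That stands as far as intent goes, and it makes the error conditional on the rule being coded as written. But the form-level sentence is the one that names items and answers, and SAP section 10 accepts self-validation for non-primary tables, so a literal coding could pass unnoticed.

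A second reply is that the cumulative opening sentence would keep these subjects in. It would, but it would also keep those stratified at month 3, whom the form-level rule drops (Step 4). It does show that repairing (a) alone leaves the section inconsistent.

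A third is that the case report forms are not in the documents. The misclassification needs the month-3 no to persist as a separate record. Protocol Table 2 schedules referral status at every follow-up visit, which supports that. Protocol 9.6 asks for the form at subsequent visits in the non-referred group unless the subject is referred, so what is recorded after referral cannot be confirmed.

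A reader might also infer that the rule understates completion of stratification. The documents do not support a direction: that follows only if the numerator yes is taken at the 12-month visit, and the numerator rule names no visit. Counted at any visit, the same rule overstates completion.

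**Conclusion.** The form-level rule for group (a) is wrong as written. It contradicts its own definition and the 6-month example, differs from the parallel implant rule, and matches no other description of the Table 4 denominator. If it is programmed literally, the 12-month proportion is wrong whenever at least one subject is referred and pending at month 3 and stratified at month 6.

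Neither direction nor size is fixed by the documents. In the regional illustration varying the month-6 share, the error runs from about 8 points too low (47.4 − 39.1) to about 33 too low (50.0 − 17.4), or from about 9 too high (56.5 − 47.4) to about 33 too high (82.6 − 50.0), depending on the numerator reading. The stratification rates and later referrals behind these figures are assumptions.

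The reach is small: one column of a secondary descriptive table. The competing-risk curve for time to the stratification visit, planned in SAP 7.9.3.3, does not use this denominator. This is a minor correction worth making before programming.

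**What to change.** In SAP 7.9.2.3:

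1. Define (a) as referred at any previous visit **and** no, or not answered, to the stratification-visit item at **all** previous visits. This is the construction of 7.9.3.3. The not-answered clause covers visits before referral.
2. State that the numerator yes is recorded at the given visit, as in the 6-month example.
3. Align the opening sentence with this definition. If a cumulative figure is also wanted, report it separately as subjects ever stratified over subjects ever referred.

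The denominator correction is one sentence; items 2 and 3 are short clarifications in the same section. No change to data collection, sample size or the primary analysis is needed.

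### SAP Table 4 scores referred subjects whose SCD risk stratification visit is still pending as not seen, and defines its denominator in two conflicting ways

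*SAP*

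**What the plan says.** SAP 7.9.2.3 describes the Table 4 denominator twice. The lead sentence is cumulative: "the denominator will be patients referred for SCD risk stratification up to the given visit". The CRF-based definition that follows has two limbs. Limb (a) is "all patients that were referred but did not have any ICD risk stratification visit at any previous follow-up visit"; limb (b) is "all patients being referred at the given visit". Together they form a set of subjects still at risk, which drops those already stratified.

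The numerator rule covers both limbs: "The subjects included in the numerator will be all subjects part of the denominator" and who have a yes to the CRF item on whether the SCD visit was performed. No minimum time since referral is required. The worked 6-month example follows the two-limb version, because it carries forward "all patients who were referred but did not have their SCD risk stratification visit within the 3 months visit window".

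SAP 7.9.3.3 builds the indicated-population column of Table 6 in the same way. Its limb (b) is "all patients meeting an indication for implant at the given visit", and the numerator is implants at that visit.

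Protocol 9.7 has subjects normally leave once the 12-month follow-up is complete, and states: "Upon exiting from the study, no further study data will be collected or study visits will occur for the subject".

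**The concern.** Referral and the stratification visit are successive steps. A subject referred at a study visit often cannot yet have been stratified when that visit's CRF is completed. Timing makes this likely at 3 months. Protocol 9.6.1 asks that the 3-month LVEF of a revascularised subject be taken at least 90 days after revascularisation, and the window closes at day 120 after the MI. If revascularisation was on or after the day of the MI, an in-window referral triggered by that LVEF leaves at most about 120 − 90 = 30 days.

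Table 4 is the only planned proportion for the step from referral to stratification. If it mixes waiting subjects with non-attenders, a working pathway can look like a failing one, and regions can differ because of appointment timing alone. With two denominators in one section, two programmers could also report different percentages from the same data. The SAP takes the second population of Table 5 from this numerator, so the ambiguity carries over.

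**Working it through.** **The plan's own figure.** SAP 6.1 needs 54 subjects per region with a reason for referral. With p = 0.70, the exact binomial probability that the Wilson 95% half-width is at most 0.125 is 0.784 for n = 53 and 0.897 for n = 54, so 54 reproduces. Then 54/0.30 = 180 and 180/0.90 = 200. The figure is used here only for scale: 54 × 0.70 = 37.8, about 38 referred per region at 3 months. The SAP states no expected value for Table 4.

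**Illustration 1.** Assumed, not in the documents: 6 new referrals at 6 months and 3 at 12 months; 80% of referred subjects seen by the next study visit; nobody seen in the window of referral; no deaths or exits.

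Under limbs (a)+(b):
- 3 months: 0/38 = 0%.
- 6 months: 0.8 × 38 = 30.4 seen; 30.4/(38 + 6) = 69%.
- 12 months: carried forward are 38 − 30.4 = 7.6 earlier non-attenders and the 6 referred at 6 months; the denominator is 7.6 + 6 + 3 = 16.6. If the 7.6 never attend, 0.8 × 6 = 4.8 and 4.8/16.6 = 29%. If they also attend at 80%, 0.8 × 13.6 = 10.88 and 10.88/16.6 = 66%.

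Under the lead sentence, the 12-month denominator is 38 + 6 + 3 = 47:
- If the 7.6 never attend: (30.4 + 4.8)/47 = 35.2/47 = 75%.
- If they attend at 80%: (30.4 + 10.88)/47 = 41.28/47 = 88%.

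The same subjects therefore read 75% or 29% in the first case, and 88% or 66% in the second. In the first case 35.2/44 = 80% of those referred by 6 months were stratified, and no (a)+(b) column shows that.

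**Some stratified in the window of referral.** Keep overall attendance at 80%, with the 7.6 never attending. If 30% of referrals are seen in the same window:
- 3 months: 30%.
- 6 months: (0.5 × 38 + 0.3 × 6)/(0.7 × 38 + 6) = 20.8/32.6 = 64%.
- 12 months: (0.5 × 6 + 0.3 × 3)/(7.6 + 0.7 × 6 + 3) = 3.9/14.8 = 26%.

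For same-window shares of 10% to 30% the columns read 10–30%, 68–64% and 28–26%.

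**Illustration 2, without non-attenders.** Assume 10 new referrals at each of 6 and 12 months, every pending subject seen by the next visit, and no deaths or exits.

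| Same-window share | 3 months | 6 months | 12 months |
|---|---|---|---|
| 0 | 0/38 = 0% | 38/48 = 79% | 10/20 = 50% |
| 0.5 | 19/38 = 50% | (19 + 5)/(19 + 10) = 83% | (5 + 5)/(5 + 10) = 67% |

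In both rows all 48 subjects referred at 3 or 6 months are seen by 12 months. The whole shortfall is pending subjects, and it disappears only if every referral is stratified in its own window.

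**The case against.** A reader might infer that subjects referred at a visit must be scored as failures, so that the 3-month column is near zero by construction. The documents do not support that. The CRF item asks whether the subject has been referred or invited, so referral can precede the study visit. Several referral reasons are clinical events that can arise between visits. The SAP's 6-month example presupposes that some subjects are stratified within the 3-month window, and a same-visit yes counts in the numerator.

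A reader might also infer that 12-month referrals can never be scored, or that no rule covers them. There is a rule: they count as seen if the visit was done by the 12-month record, and Protocol 9.3 (Table 2) also marks referral status at study exit. Only those still pending then remain uncorrected.

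Three further points carry weight.
- Attendance at stratification is not a listed objective. Table 4 is a descriptive step towards indication, which Table 5 also reports for the Enrolled Population.
- SAP 7.9.3.3 already plans a competing-risk curve for the stratification visit, with mortality accounted for. Its clock starts at enrollment, so it does not give attendance or delay after referral.
- Table 4 prints counts, so a reader could rebuild the overall share: in Illustration 1, (0 + 30.4 + 4.8)/44 = 80%. That works when nobody dies or exits; the SAP does not say whether pending subjects who do so stay in the next denominator.

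**Conclusion.** The point holds as a defect of definition and presentation in a secondary descriptive table. Pending subjects are scored as not seen, no column gives the overall share stratified, referrals pending at the end are not corrected, and the two denominators disagree.

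The size is not known. It depends on the same-window share, the later referrals and the attendance rate, none of which the documents give. It would be wrong to cite 29% at 12 months as the expected distortion: that figure requires earlier non-attenders never to attend, and it becomes 66% if they attend at the same 80%. The conflict between denominators remains in both cases (75% against 29%, 88% against 66%). The primary proportion in Table 3 and the sample size are unaffected.

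**What to change.** 1. Define Table 4 cumulatively. At each visit the denominator is all subjects ever referred up to that visit, and the numerator is those ever stratified up to that visit. Split the remainder into pending, died or exited, and refused or not attended where recorded. Delete the conflicting definition.
2. Beside the planned curve from enrollment, add a cumulative incidence curve from referral date to SCD visit date, with death as a competing event and censoring at exit.
3. Keep subjects first referred at 12 months, score them from the 12-month or exit record, and show how many are pending. Dropping them would discard subjects already stratified. It would also discard some late 6-month referrals, because SAP 5.1 counts a referral at an out-of-window visit at the next visit.
4. Treat the indicated column of Table 6 likewise: cumulative indicated and implanted, plus time from indication to implant. Leave its Enrolled Population column unchanged.

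The cost is SAP wording and a little programming; the planned curves already need these event dates. Subjects referred late will contribute little follow-up to the new curve.
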